### Sample Size Calculations and Power

In designing this study, we adhered to the criteria of the PCORI methodology principals that pertain to the development of research questions.iii We used preliminary studies to estimate that approximately 80% of the eligible adolescents would agree to participate. The goal was to enroll a total sample of **1400** sexually active Latina girls aged 14-18 in the study (700 per treatment group). Sample size estimates and power analyses were based on a 40% attrition rate by the 3-month follow up (**840** total, 420 per treatment group) and another 10% by the 6-month follow-up (**700** total, 350 per treatment group).

Assuming power = .80 and alpha = .05, the minimum detectable difference in the primary behavioral outcome at each time point between the intervention and the control condition is 12-14, 18-19 or 22-23 percentage points depending on whether the intraclass correlation (ICC) assessing the

clustering effect of clinics is low, moderate, or high. Prevalence of outcomes in the control condition come from the final data set after completion of data collection, and the ICC range is suggested by data from Reading et al.iv The calculated differences in proportions translate into an effect size (Cohen’s h) falling between a small (h=.20) and medium (h=.50) effect size for all three levels of ICC. Specifically, regarding evaluation of the intervention condition, the minimum achievable precision for point estimates of proportions is a confidence interval width of 11 percentage points for visit data, and 12 percentage points for 3-month data and 6-month data.

The calculated differences in proportions translate into an effect size (Cohen’s h) falling between a small (h=.20) and medium (h=.50) effect size for all three levels of ICC. Specifically, regarding evaluation of the intervention condition, the minimum achievable precision for point estimates of proportions is a confidence interval width of 11 percentage points for visit data, and 12 percentage points for 3-month data 6-month data.

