## Study Overview

A cluster randomized controlled trial of 18 school based health centers (SBHCs) with 1,360 Latina adolescents evaluated the extent to which the app: (1) supports adolescents in making decisions about an effective method of contraception; (2) improves the effectiveness and efficiency of the clinical encounter; and (3) reduces the incidence of unprotected sexual intercourse among Latina adolescent girls over time. The long term goal of the intervention is to reduce health disparities in unintended pregnancy rates for Latina adolescents. Clinics provided all adolescent girls with an iPad. The iPad assessed eligibility and obtained consent. Participants in the nine intervention clinics received the app and those from nine control clinics received standard of care sexual health questions. In addition to the baseline, pre-visit questionnaire, participants were asked to complete follow-up surveys within 48-hours, 3 and 6 months after the visit. Differences in adolescents' contraceptive knowledge, attitudes, self-efficacy and use over the 6-month follow up was assessed by generalized mixed effects models that to account for repeated measures, a time effect, the time by group interaction, and demographic covariates.

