## Participants

Participant recruitment began in August 2016 and continued through May 2018. All adolescent girls ages 14- 18 years who visited any of the participating SBHCs, regardless of reason for visit, were invited to use an iPad with the web application. The computer assessed eligibility of the teens using an online screener built in to the app. The inclusions criteria for the study is outlined below.

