### Analytical and statistical approaches

We assessed the effect of the intervention by looking for differences over time between the control (usual care) group and intervention (Health-E You app) group in contraception use self-efficacy and self-reported use of non-barrier contraception at follow-up. Specifically we hypothesized, assuming group equivalence at baseline, that 3 months and 6 months post-baseline the intervention group, compared to the control group, would have higher mean contraception use self-efficacy (Aim 1c, Primary Outcome 2) and a higher proportion would be using effective (i.e., non-barrier) contraception (pill, patch, ring, shot, IUD, or implant) (Aim3b, Primary Outcome 3).

We assessed the effect of the intervention using generalized mixed effects models estimated by maximum likelihood (mixed effects linear regression to assess self-efficacy, mixed effects logistic regression to assess non-barrier contraception use). These models included the repeated outcome measure as the response variable as well as terms for the intercept, an indicator of treatment of group (intervention vs. control), a time effect (baseline, 3-month follow-up, 6-month follow-up), the time by treatment group interaction, and three covariates that clinical experience and thre research literature suggest could influence the outcome: age (rage was 14-18), whether the purpose of the clinic visit was related to pregnancy or contraception (a time invariant covariate), and whether the participant engaged in sexual intercourse in the past 3 months (a time varying covariate). We fit models with random intercepts and slopes over time to accommodate the repeated measures gathered from each subject and to allow subject-specific changes in the responses over time. The time treatment group interaction was the direct test if the intervention effect. Computation of p-values was based on robust variance estimation that adjusted for a potential lack of independence between observations due to clustering by recruitment site (SBHC).

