#### Heterogeneity of Treatment Effects

A concern in any cluster randomized control trial is whether or not the treatment effect is robust across sites. However, small per site sample sizes preclude direct comparisons between sites because of a lack of statistical power. We investigated the sensitivity of the intervention effect to recruitment site (SBHC) in the two primary outcomes where we assessed changes from baseline to

3-month and 6-month follow-up: contraception use self-efficacy (Aim 1c, Primary Outcome 2) and non-barrier contraception use (Aim 3b, Primary Outcome 3). For both outcomes, the time by treatment group interaction served as the direct test of the intervention effect. With three time points and two treatment groups, the interaction was represented by two parameter estimates. The sensitivity analysis employed a jack-knife technique where the analysis is repeated but with participants from one intervention SBHC removed from the analysis. Since there were 9 SBHCs randomly assigned to each treatment group, the jack-knife technique required 9 new models be assessed.

Table 2 reports the point estimate, 95% confidence interval, and p-value for each parameter obtained from the mixed effects regression analysis model including all 9 intervention SBHCs plus the range of parameter estimates and p-values obtained from the jack-knife analyses (models that included only 8 intervention SBHCs).

**Table 2. Parameter Estimates from Sensitivity Analyses Compared to Parameter Estimates from Analytic Models for Two Primary Outcomes**

Outcome	Interaction Parameter	Estimate	Analytic Model		Sensitivity Analyses	
			95% CI	p-value	Estimates	p-value
Contraception Use Self-efficacy	1	0.816	-0.482, 2.115	.218	0.477-1.086	.098-.408
	2	1.576	0.377, 2.774	.010	1.269-1.729	.006-.037
Non-barrier Contraception	1	1.190	0.043, 2.338	.042	1.128-1.350	.024-.063
	2	1.711	0.529, 2.544	.005	1.511-1.936	.003-.012

For both outcomes, the data suggest the intervention effect is not sensitive to recruitment site (SBHC).

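### Table 1's detectable differences assume 18 equal-sized clinics and normal quantiles; with 9 clinics per arm they do not give 80% power at a true 5% level

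*Combined protocol and SAP*

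**What the plan says.** All places are in the combined protocol and SAP.

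- **Design.** The Study Overview describes "A cluster randomized controlled trial of 18 school based health centers (SBHCs) with 1,360 Latina adolescents". Heterogeneity of Treatment Effects adds "Since there were 9 SBHCs randomly assigned to each treatment group".
- **Enrolment.** Under Participants, all girls aged 14-18 "who visited any of the participating SBHCs, regardless of reason for visit, were invited". No quota or target per clinic is given.
- **Power.** Sample Size Calculations and Power gives the detectable differences in these terms: "Assuming power = .80 and alpha = .05, the minimum detectable difference in the primary behavioral outcome at each time point". Table 1 lists the analysed N, the control proportion and the change with Cohen's h for each outcome and ICC. The text says that h lies between .20 and .50 at all three ICCs. It also says: "Prevalence of outcomes in the control condition come from the final data set after completion of data collection".
- **Test.** Analytical and statistical approaches says: "Computation of p-values was based on robust variance estimation that adjusted for a potential lack of independence between observations due to clustering" by clinic. The two visit outcomes likewise use robust variance.

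Neither the power section nor the analysis section mentions variation in clinic size, degrees of freedom or a small-sample correction.

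**The concern.** In a cluster trial with 18 clinics, the treatment effect is judged against variation between clinics, and that variation is estimated from few units. A calculation with normal quantiles treats it as known. A calculation with N/18 girls in every clinic also treats the clinics as equal, although girls were taken as they came. Both simplifications favour the design, and neither is disclosed.

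At stake is whether 80% power and alpha .05 hold together at the stated differences. If they do not, either the design is less sensitive than Table 1 says, or the test rejects too often under the null. A reader who uses Table 1 to judge which effects the trial could have missed would set the limit too low.

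**Working it through.** **Inputs.** 18 clinics, 9 per arm (Study Overview; Heterogeneity of Treatment Effects). From Table 1: N = 505, 616 and 669; control proportions 39%, 45% and 33%; ICC .01, .05 and .09. Alpha .05 is taken as two-sided, because one-sided 5% does not reproduce the table (visit h would be .249/.339/.410). Clinic sizes are not given.

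**Step 1: reproduce Table 1.** With equal clinics and equal arms,

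DE = 1 + (N/18 − 1) × ICC, and h = (1.960 + 0.842) × √(4·DE/N).

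Example, visit outcome, ICC .05: N/18 = 28.06; DE = 1 + 27.06 × .05 = 2.353; h = 2.802 × √(4 × 2.353/505) = .382, or 19.0 points above 39%.

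| Outcome | h computed (ICC .01/.05/.09) | h stated | Points computed | Points stated |
|---|---|---|---|---|
| Visit | .281/.382/.462 | .282/.380/.456 | 14.0/19.0/22.9 | 14/19/23 |
| 3 months | .261/.368/.451 | .26/.365/.445 | 13.0/18.2/22.2 | 13/18/22 |
| 6 months | .253/.363/.447 | .255/.361/.441 | 12.3/17.8/22.0 | 12/18/22 |

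Every h agrees within .006 and every difference after rounding. Solving the stated h for clinic size gives about 27-29, 33-34 and 36-40, against N/18 of 28.1, 34.2 and 37.2. There is no visible allowance for unequal sizes. A t reference on 16 degrees of freedom would give .299/.407/.492 for the visit row, so it was not used.

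**Step 2: change only the reference distribution.** The degrees of freedom between clinics are 18 − 2 = 16. The critical value rises from 1.960 to 2.120, and the noncentrality needed for 80% power from 2.802 to 2.985.

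| Outcome | Power at stated h (ICC .01/.05/.09) | 80%-power difference, points |
|---|---|---|
| Visit | 75.2/74.3/73.8% | 14.9/20.2/24.4 |
| 3 months | 74.7/74.1/73.8% | 13.8/19.4/23.6 |
| 6 months | 75.6/74.4/73.8% | 13.1/19.0/23.4 |

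This step needs no figure from outside the documents.

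**Step 3: which reference did the analysis use?** The first row of Table 2 separates the two. The estimate is 0.816 with interval −0.482 to 2.115, a half-width of 1.2985. With a normal reference, SE = 1.2985/1.960 = 0.6625, z = 1.23 and p = .218, as stated. With 16 degrees of freedom the same interval implies p of about .20. The next two rows also fit the normal reference (.010 and .042; on 16 degrees of freedom, .013 and .043). The fourth interval is not centred on its estimate (midpoint 1.5365 against 1.711) and cannot be used.

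Referring a statistic with 16 degrees of freedom to ±1.96 gives a true two-sided alpha of 2 × P(t16 > 1.96) = 6.8%. A beta-binomial simulation with equal clinics, a robust-variance logistic comparison and a normal reference gave 79-82% power and 7.0-7.7% type I error.

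**Step 4: unequal clinics, by assumption.** DE becomes 1 + ((1 + CV²) × N/18 − 1) × ICC. Power at the stated h with normal quantiles, over the three outcomes:

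| Assumed CV | ICC .01 | ICC .05 | ICC .09 |
|---|---|---|---|
| .4 | 78-79% | 75-76% | 74% |
| .6 | 76-77% | 71% | 69% |

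**Step 5: the statement on h.** At ICC .09 with 16 degrees of freedom, the required h is .476-.492 with equal clinics, still under .50. At an assumed CV of .4 it is .505-.520, so the statement fails for all three outcomes.

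**The case against.** The strongest reply is that the documents describe no 16-degree-of-freedom test. The plan specifies robust variance without a t correction, and Table 2 fits a normal reference. For that test with equal clinics, nominal power is near 80%. This stands. A reader might infer that the test actually used had only 74-76% power; the documents do not support that. The 74-76% belongs to a test that holds 5%. With the normal reference, the shortfall appears as type I error instead. The stated pair of 80% and .05 is missed either way.

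Second, the loss from unequal clinics rests on an unknown CV, and at ICC .01 with CV .4 it is only one or two points. This also stands. It is tempting to combine CV .6 with 16 degrees of freedom and report 63-72% power and detectable differences up to 27.3 points as what the design delivers. Those figures illustrate an assumption. The design-effect formula is also conservative if the analysis weights clinics efficiently.

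Third, Table 1 compares proportions at single time points. The models for contraceptive use add baseline, covariates and imputation, which may move power either way. So it cannot be said that the final analyses were underpowered.

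Fourth, the documents report no null result for a Table 1 outcome: the non-barrier rows of Table 2 have p = .042 and .005. Harm from over-reading a null result is therefore hypothetical here.

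Finally, Table 1 contains no arithmetic slip. It is right on its own inputs, and the formula behind it is inferred from the close match.

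**Conclusion.** The point holds as a fault in unstated assumptions. The stated differences do not go with 80% power at a true 5% level. With equal clinics the cost is about 5 points of power, or detectable differences roughly 1 to 1.5 points larger; if a normal reference is kept, it is a true alpha of about 6.8% instead of 5%. This part rests only on 9 clinics per arm and Table 1's own inputs.

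Unequal clinic sizes add to the loss. The direction is safe, since enrolment had no clinic quota and equal analysed numbers in all 18 clinics are implausible. The amount depends on an unreported CV and matters mainly at ICC .05 and .09. That the analysis used a normal reference is inferred from three rows of Table 2, which do not cover the visit outcomes. The conclusion concerns the cross-sectional calculation in Table 1 and does not extend to the power of the final models.

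**What to change.** 1. Report the analysed girls per clinic, or their CV, by arm and time point. Clinic membership is already used in the imputation and jack-knife, so the data are held.
2. Recompute Table 1 and the statements under Sample Size Calculations and Power, including the one that h lies between .20 and .50, with that CV and a t reference on 16 degrees of freedom. State both assumptions.
3. Use the same 16-degree-of-freedom reference, or a small-sample-corrected robust variance, for the clinic-clustered p-values and intervals in Analytical and statistical approaches and in Table 2, so that the power table and the analysis agree. If clinic sizes differ widely, the corrected variance is safer: in the simulation, the t reference alone gave 5.2-5.8% type I error with equal clinics but 6.9-8.0% at CV .65.

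Enrolment does not change. The cost is a recalculation, somewhat less favourable detectable differences and wider intervals. As an example, keep the standard error implied by the first non-barrier row of Table 2, (2.338 − 0.043)/(2 × 1.96) = 0.585, and change only the reference. Then t = 1.190/0.585 = 2.03 on 16 degrees of freedom, p moves from .042 to about .059, and the interval becomes about −0.05 to 2.43. This shows what the choice of reference can do; it does not replace a refit.

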**Table 1: Power Analysis**

Outcome	Minimum detectable change if:				
	% of Baseline Sample (N)	Control Proportion	ICC=.01 Change (h)	ICC=.05 Change (h)	ICC=.09 Change (h)
Receive effective method at visit*	37% (505)	39%	+14% (.282)	+19% (.380)	+23% (.456)
Use effective method at 3 months	45% (616)	45%	+13% (.26)	+18% (.365)	+22% (.445)
Use effective method at 6 months	49% (669)	33%	+12% (.255)	+18% (.361)	+22% (.441)

\* Analysis is limited to participants not already using an effective contraceptive method.

### Time Frame for the Study

Participant recruitment took place from August 2016 to May 2018 and was most active during the school year when SBHCs were fully operational. Recruitment continued during the summer months, but was limited due to staffing and fewer students on campus. Follow-up procedures continued through December 2018.

To evaluate the effectiveness of the app, the research team compared differences between the intervention and control group prior to the intervention (at baseline), within 48 hours of the visit and at 3-month and 6-month follow-up periods. These follow-up time points were selected for a number of reasons. Oral contraceptives are the most commonly used non-barrier contraceptive, and they have high rates of discontinuation within the initial 3-month period.v In addition, unprotected sex

among adolescents, including use of the withdrawal method, is high.vi Furthermore, while there is little research on discontinuation rates for LARCs, a recent study (among women 25 years and younger) found that discontinuation rates are generally low and do not vary much between 6 and 12 months, thus a 6-month follow-up was deemed adequate.vii

### Data Collection and Sources

Follow-up procedures are designed to maximize participant retention over time and minimize bias due to attrition. Youth were informed that they would receive a financial incentive of up to US\$70 for completing all follow-up surveys. The following is the incentive structure:

- US\$10 for completing the baseline information and immediate follow-up survey,
- US\$20 for completing the 3-month follow-up assessment,
- US\$20 for completing the 6-month follow-up,
- US\$20 bonus for completing all surveys.

Participants were enrolled in the study for a total of six months (with one additional month to complete follow-up surveys) following their initial clinic visit, where they interacted with our Health-E You app or completed the baseline survey. We also collected the youth's preferred method of contact (e-mail and, or cell phone) to provide them with their follow-up surveys and e-gift cards. We also explained that their participation was completely confidential.

Each participant was sent their survey link by email and / or text. Non-respondents received up to three reminders to complete their follow-up survey. Those who provided phone information were also contacted by phone to either complete the survey immediately by phone or to have the link resent to them. Participants had one week to complete the immediate follow-up survey and up to 30 days to complete the 3 and 6 month follow-up surveys. In addition, we designed our follow-up surveys so that we can capture data from participants who did not respond to previous follow-up surveys. This was an additional strategy to reduce our overall attrition.

We were unable to ascertain exactly why individual participants were lost to follow-up because of the remote nature of the study. However, while conducting follow-up procedures, our team noted that many phone numbers had changed or were no longer valid, or e-mails bounced back. This population is of Latina background and we heard two issues that impacted the study. One is that participants return to visit family members in Mexico for extended time periods. Another was concerns over immigration “crackdowns” and were worried that sharing contact information may put family members and/or friends at risk – regardless of the participant’s immigration status.

### Analytical and statistical approaches

We assessed the effect of the intervention by looking for differences over time between the control (usual care) group and intervention (Health-E You app) group in contraception use self-efficacy and self-reported use of non-barrier contraception at follow-up. Specifically we hypothesized, assuming group equivalence at baseline, that 3 months and 6 months post-baseline the intervention group, compared to the control group, would have higher mean contraception use self-efficacy (Aim 1c, Primary Outcome 2) and a higher proportion would be using effective (i.e., non-barrier) contraception (pill, patch, ring, shot, IUD, or implant) (Aim3b, Primary Outcome 3).

We assessed the effect of the intervention using generalized mixed effects models estimated by maximum likelihood (mixed effects linear regression to assess self-efficacy, mixed effects logistic regression to assess non-barrier contraception use). These models included the repeated outcome measure as the response variable as well as terms for the intercept, an indicator of treatment of group (intervention vs. control), a time effect (baseline, 3-month follow-up, 6-month follow-up), the time by treatment group interaction, and three covariates that clinical experience and thre research literature suggest could influence the outcome: age (rage was 14-18), whether the purpose of the clinic visit was related to pregnancy or contraception (a time invariant covariate), and whether the participant engaged in sexual intercourse in the past 3 months (a time varying covariate). We fit models with random intercepts and slopes over time to accommodate the repeated measures gathered from each subject and to allow subject-specific changes in the responses over time. The time treatment group interaction was the direct test if the intervention effect. Computation of p-values was based on robust variance estimation that adjusted for a potential lack of independence between observations due to clustering by recruitment site (SBHC).

We also hypothesized that mean contraception use self-efficacy would be higher in the intervention group than the control group immediately after the clinic visit (Aim 1b, Primary Outcome 1). The same analytic approach already described was implemented to assess this hypothesis with the exception that the mixed effects linear regression model included only two time points: baseline and 48 hours after baseline (which changed the sexual activity covariate to being time invariant).

Among intervention group participants only contraception knowledge was assessed immediately prior to using the *Health-E You* app and immediately after app use. We predicted mean knowledge would increase from the pre-app assessment to the post-app assessment (Aim 1a, Secondary

Outcome 1). Once again, a mixed effects linear regression analysis was employed with two time points, the same covariates, and robust variance estimation (to account for clustering by SBHC). However, since the control group was not part of the analysis, the model did not include parameters representing treatment group or the time by treatment group interaction. In this model, the time parameter was the direct test of the intervention effect.

Finally, we hypothesized that at the clinic visit (the visit immediately following recruitment and, in the intervention condition, use of the app) a higher proportion of the intervention group, when compared to the control group, would discuss birth control with the clinician (Aim 2b, Secondary Outcome 2) and receive a non-barrier method of birth control either directly or via an appointment or referral (Aim 3a, Secondary Outcome 3). These hypotheses were tested using logistic regression models regressing the dichotomous (yes-no) outcomes on treatment group (the direct test of the intervention effect), age, purpose of visit, and whether sexually active in the prior 3 months using robust variance estimation (to account for clustering by SBHC).

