#### Exclusion criteria

Adolescents were not eligible to participate in the study if they were:

- Not biologically female
- 13 years or younger or 19 years or older
- Did not identify as Hispanic/ Latina
- Used the app outside of a participating SBHC appointment
- Not sexually active
- Pregnant at the time of screening
- Using a LARC method of contraception at the time of screening
- Did not complete the intervention or baseline questionnaire

SBHCs were randomly assigned, at equal chance, to either the intervention (*Health-E You/Salud iTu* app) or control group (standard of care, no app). This design allows our analyses to isolate the effect of the app and determine whether the app increases adolescent sexual health and contraceptive knowledge, self-efficacy in selecting an effective method, satisfaction with the visit and contraceptive use and adherence over time.

Clinics were randomized to either control or intervention group using computer-generated random number assignment. Following randomization, our local partners from The Los Angeles Trust for Children’s Health (LA Trust) notified the SBHCs of their assignment and provided the necessary training around the study aims, use of the iPad and integration into the unique workflow at each SBHC (determined in partnership with our community outreach staff and clinic staff, providers and managers). The LA Trust also provided technical support to ensure that all sites had a reliable internet connection to be able to use the app as intended and to securely transmit data gathered from the app to the University of California, San Francisco (UCSF).

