#### Handling Missing Data

Since each assessment involves a relatively brief self-administered instrument, the amount of missing data due to failure to provide data was minimal. The largest source of missing data was participant dropout. Of the 1360 participants in the study cohort 778 (57.2%) responded to the 48-hour survey, 681 (50.1%) responded to the 3-month survey, 676 (49.7%) responded to the 6-month survey, and 575 (42.3%) responded to both the 3-month survey and the 6-month survey.

Consequently, to minimize bias due to attrition, we employed multiple imputation so that every regression model could be fit to all available data while invoking the mild assumption that the data were missing at random. Imputation was performed on the data in wide format (one record per case) to correctly account for dependence in multiple observations per case. In models testing a time by treatment group, missing data were imputed separately for intervention cases and control cases. Imputation models contained all variables in the analysis model (including the outcome), baseline variables identified as correlates of retention, and indicator variables representing recruitment site (SBHC).

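### The 3- and 6-month models for Primary Outcomes 2 and 3 adjust for sexual activity measured after app use, so their interaction terms need not estimate the total effect of assignment

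*Combined protocol and SAP*

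**What the plan says.** The section on analytical and statistical approaches describes mixed models with three time points for self-efficacy and non-barrier use. Besides group, time and their interaction, they contain age, whether the visit concerned pregnancy or contraception, and "whether the participant engaged in sexual intercourse in the past 3 months (a time varying covariate"). The stated reason is that clinical experience and the literature suggest these factors could influence the outcome. For both outcomes, according to the section on heterogeneity of treatment effects, "the time by treatment group interaction served as the direct test of the intervention effect".

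The same analysis section says that activity becomes time invariant in the model with only baseline and 48 hours. This confirms that it is updated at 3 and 6 months in the other two models, and it leaves Primary Outcome 1 outside this point.

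On the target, the hypotheses compare intervention with control at 3 and 6 months, with no condition on current activity. The text on allocation under the exclusion criteria adds: "This design allows our analyses to isolate the effect of the app". The Study Overview summarises the models as containing "a time effect, the time by group interaction, and demographic covariates". Aim 3b refers to sexually active adolescents; the inclusion criteria define that as having had intercourse, which every participant meets at entry.

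**The concern.** A covariate recorded after assignment can itself respond to the intervention. Adjusting for it removes any part of the effect that runs through it. It can also create an association between arm and outcome when the covariate and the outcome share unmeasured causes. For non-barrier use the covariate covers the same three months as the outcome. The stated reason, that activity could influence the outcome, supports adjusting for a baseline value; it does not deal with a value recorded after app use.

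At stake is what the four interaction estimates in Table 2 mean. If recent activity differs by arm because of the app, they need not be the total effect of assigning clinics to it. The documents report no activity by arm at follow-up and no version of either model without the updated covariate. The jack-knife removes one intervention clinic at a time and leaves the covariates as they are.

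**Working it through.** **1. The plan's own yardstick.** No figure in the plan is disputed; Table 1 supplies control proportions and a scale. Its detectable differences reproduce with n_eff per arm = (N/2) / [1 + (N/18 − 1) × ICC] and h = (1.960 + 0.842) × √(2/n_eff), back-transformed by arcsine.
- "Use effective method at 3 months", N = 616, ICC .01: design effect 1 + (34.22 − 1) × 0.01 = 1.332; n_eff = 308/1.332 = 231; h = 0.261 (stated .26); 13.0 points. At ICC .05 and .09: 18.2 and 22.2. Stated: 13, 18, 22.
- "Use effective method at 6 months", N = 669, ICC .01: design effect 1.362; n_eff = 334.5/1.362 = 246; h = 0.253 (stated .255); 12.3 points. At ICC .05 and .09: 17.8 and 22.0. Stated: 12, 18, 22.

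**2. Hand calculation, non-barrier use.** From Table 1: control use 45% at 3 months. Assumed: 75% of controls recently active; use higher by 20 to 35 points among the active; arm difference in activity 5 to 10 points. Shift = arm difference × difference in use:
- 0.05 × 20 = 1.0; 0.05 × 35 = 1.75; 0.10 × 20 = 2.0; 0.10 × 35 = 3.5 points.

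Example with a 35-point difference and no app effect on use except through activity. Use among the inactive is 45 − 0.75 × 35 = 18.75%.
- App-arm activity 65%: use is 18.75 + 0.65 × 35 = 41.5%. The total effect is −3.5 points, the adjusted effect 0, the shift +3.5.
- App-arm activity 85%: use is 18.75 + 0.85 × 35 = 48.5%. The total effect is +3.5, the adjusted effect 0, the shift −3.5.

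**3. Model fits.** Large-sample logistic fits with random intercepts and slopes used control use of 45% and 33% (Table 1) and interactions of 1.19 and 1.71 (Table 2). Assumed: baseline use 30%; activity 75%; activity odds ratio 2, 3 or 5.67; intercept SD 1 to 1.5; slope SD 0.3 to 0.5; intercept related or unrelated to activity. Standardised difference from the time-varying model minus the true total, in points:

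| App-arm activity | 3 months |
|---|---|
| 5 points lower | +0.6 to +2.0 |
| 5 points higher | −0.6 to −1.7 |
| 10 points lower | +1.1 to +3.8 |
| 10 points higher | −1.1 to −3.5 |

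At 6 months the absolute shift is 0.5 to 1.8 (5-point difference) and 1.0 to 3.4 (10-point difference). Limits: no clustering, no imputation, and no effect of method use on activity.

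**4. The direction is not fixed.** A separate simulation with one follow-up time gave the app no effect on use and activity no effect on use, but let the two share an unmeasured cause. Activity was 67% in control and 51% in the app arm. With a common cause acting in the same direction on both, the true difference was 0.002 and the adjusted one 0.027 (shift +2.5 points). With opposite directions they were 0.000 and −0.026 (shift −2.6). Across all its settings, with arm differences in activity of 13 to 19 points, the shift ran from −4.5 to +5.5 points.

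**5. No arm difference in activity.** The shift was at most 0.1 point in the simulation of step 4, and the time-varying version stayed within 0.32 points of the true total in the fits of step 3. Log-odds coefficients can still move. In one setting with 67% active in both arms, the log odds ratio was 0.52 unadjusted and 0.59 adjusted, while both versions gave a difference in proportions of 0.128. That is non-collapsibility, not bias.

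**6. Self-efficacy (scale 0 to 30).** Assumed: 1 to 3 points' difference in score by activity. Shift: 0.05 × 1 = 0.05 to 0.10 × 3 = 0.30 points, up or down. Table 2 estimates: 0.816 and 1.576.

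**The case against.** The strongest reply is that nothing suggests the app changes sexual activity. It is a contraceptive decision aid, no listed outcome is frequency of intercourse or abstinence, and Aim 3 is measured only through receipt and use of methods. Without an effect on activity there is essentially no bias, and even with one, activity must also affect the outcome or share causes with it. This stands, and it keeps the point conditional.

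Second, recent activity determines contraceptive need in the outcome's own window, and the analysis section elsewhere uses *sexually active* for the prior three months. An effect conditional on current activity is therefore a possible reading of Aim 3b. But no section defines that effect, and Aim 3b does not cover self-efficacy.

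Third, the overview's description of the covariates is shorthand (visit purpose is not demographic either), and the sentence on isolating the app's effect describes allocation. Both are fair; the point rests on the hypotheses and the model description.

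A reader might infer more from three things:
- **Missing data.** The surveys missing at 3 months (1,360 − 681 = 679) and 6 months (1,360 − 676 = 684) also carry the outcome, which is imputed whichever version of the covariate is used. They add nothing here.
- **Significance.** Non-barrier parameter 1 (p = .042) is borderline, but no re-fit with its own standard error shows it would cross .05, and a crossing would not by itself show bias.
- **Direction.** That lower activity in the app arm means an overstated effect holds only if activity and use are positively associated; step 4 gives a counterexample.

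**Conclusion.** The concern holds as a conditional one. The two models adjust for a variable recorded after app use, while the stated hypotheses are about groups as assigned. If the app changes recent activity, and activity affects the outcome or shares causes with it, the interaction is biased for the total effect of assignment, upward or downward.

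On the assumptions shown, a 5 to 10 point arm difference in activity shifts the effect on non-barrier use by roughly 0.5 to 4 points, against Table 1 detectable differences of 12 to 22 points. It shifts self-efficacy by 0.05 to 0.30 points. With no arm difference in activity the shift is about zero. These figures illustrate scale; they do not estimate bias in this trial.

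A reader might go on to infer that the Table 2 effects are overstated or wrong. The documents do not support that, because they contain no follow-up activity by arm. Confidence is high that the covariate is updated after app use and that the conditional effect is undefined; the consequence for Table 2 is unknown.

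**What to change.** 1. Fit both models with the baseline value of past-3-month intercourse, or without it, as the estimate of the total effect of assignment. The baseline value should be on record for everyone, since the exclusion criteria remove those who "Did not complete the intervention or baseline questionnaire".
2. Keep the time-varying version beside it as a labelled sensitivity analysis. Disclose the change as post hoc, because the Table 2 results are already known.
3. Report past-3-month intercourse by arm at 3 and 6 months. If the arms are similar and the two versions agree, the concern is largely answered.
4. For non-barrier use, give standardised differences in proportions for both versions, so that a change in log-odds due only to non-collapsibility is not read as bias.

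Follow-up activity may stay in the imputation model, where it already belongs under the current rule: "Imputation models contained all variables in the analysis model (including the outcome").

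Cost: no new data, two re-fits, one descriptive table, standardised differences for one outcome and a disclosure sentence. The downside is possibly slightly less explained variance.
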